7.1 Sample Size Determination

The determination of sample size was based on a review of similar cataract and dry eye studies. As this is a single center, pilot study, it was determined that a sample size of 40 patients would be feasible.

7.2 Statistical Methods

An ANOVA analysis will be performed to compare the dry eye testing data between the DEXYCU group and the standard regimen group.

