3.1 General Design

- The type/design of the study:
 - Prospective randomized controlled trial
- A description of the measures taken to minimize/avoid bias:
 - Patients undergoing bilateral cataract surgery will be randomized to the DEXYCU group (standard postoperative cataract regimen + intraoperative DEXYCU) in one eye or the STANDARD group (standard postoperative cataract regimen). Randomization will be done after screening visit, prior to surgery on the first eye and will be done by coin flip. Standard cataract regimen to be used: topical prednisolone acetate 1% qid and topical gatifloxacin qid for 1 week, then tid for 1 week, then bid for 1 week.
- Expected duration of subject participation
 - 3 weeks after cataract surgery
 - Patients undergoing cataract surgery will have dry eye testing prior to surgery, 1 week after surgery, and 3 weeks after surgery
- A summary description of the sequence and duration of all trial periods including follow-up, if any
 - Patients undergoing cataract surgery will have dry eye testing prior to surgery, 1 week after surgery, and 3 weeks after surgery

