3.2 Primary/Secondary Endpoints

Primary endpoints:

- 1) Tear film Osmolarity as measured on Tear Lab system
- 2) Corneal Staining (Oxford grading scale 0-15)

Secondary endpoint:

- 3) Satisfaction questionnaire – How satisfied are you with your surgery? (Graded 0-4)

4 Subject Selection and Withdrawal

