4.3 Subject Recruitment and Screening

Subjects will be recruited for the study from principal investigator's clinical practice. As part of the informed consent process, patients will be offered a DEXYCU injection and given a brochure/handout discussing DEXYCU. As part of the standard cataract evaluation process, both tear film osmolarity and corneal staining will be performed.

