5.3 Method for Assigning Subjects to Treatment/Dosing Groups

Patients undergoing bilateral cataract surgery will be randomized to the DEXYCU group (standard postoperative cataract regimen + intraoperative DEXYCU) in one eye or the STANDARD group (standard postoperative cataract regimen). Randomization will be done after screening visit, prior to surgery on the first eye and will be done by coin flip. Patients who are randomly assigned to the DEXYCU group will receive a sequentially numbered drug kit.

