5.6 Packaging, Receiving, Storage, Dispensing and Return

Dexycu will be stored in a locked cabinet. Usage of the medication will be logged.

6 Study Procedures

- Screening Visit
- Day 1 Postoperative Visit
- Day 7 Postoperative Visit
- Day 21 Postoperative Visit

At all visits, visual acuity, eye pressure measurements, tear film osmolarity, and corneal staining will be measured and recorded. At days 7 and 21, patient satisfaction scores will be measured.

7 Statistical Procedures

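### Section 7.2 specifies no baseline adjustment in the ANOVA, although both primary measures are recorded at screening; ANCOVA would probably give narrower intervals from the same 40 patients

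*Combined protocol and SAP*

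**What the plan says.** Section 7.2 is a single sentence: "An ANOVA analysis will be performed to compare the dry eye testing data", with DEXYCU and the standard regimen as the two groups. It names no covariate or visit, and does not say whether follow-up values or changes from baseline are compared.

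The baseline data exist. Section 3.2 makes tear film osmolarity and a 0-15 corneal staining grade the two primary endpoints. Section 6 lists screening among the four visits and states: "At all visits, visual acuity, eye pressure measurements, tear film osmolarity, and corneal staining will be measured and recorded". Section 4.3 agrees: "As part of the standard cataract evaluation process, both tear film osmolarity and corneal staining will be performed". Section 5.3 puts allocation after these measurements: "Randomization will be done after screening visit, prior to surgery on the first eye and will be done by coin flip". No stratification is described.

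Section 7.1 justifies the number of patients by feasibility: "As this is a single center, pilot study, it was determined that a sample size of 40 patients would be feasible". It gives no SD, effect size, alpha or power.

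**The concern.** A screening value of the same measure, taken before allocation, is usually the most useful covariate a small trial has. If section 7.2 means an ANOVA of post-operative values, that information is unused. The interval is then wider than the data require whenever screening and follow-up values are more than weakly correlated.

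The coin flip balances baseline only on average. In the one trial that is run, a chance difference in screening osmolarity or staining carries through to the unadjusted estimate in proportion to the correlation. If section 7.2 means change scores instead, baseline is used but with a fixed weight. At a low correlation that is worse than ignoring it.

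With the sample fixed by feasibility, analysis is one of the few places where precision can still be gained. Validity is not at stake: under randomisation the unadjusted comparison is unbiased on average and keeps its type I error.

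**Working it through.** **Inputs.** From the documents: 40 patients (7.1), two groups (7.2), both primary measures at screening (4.3, 6), allocation afterwards by coin flip (5.3). The sample size of 40 cannot be reproduced, because section 7.1 gives nothing to calculate it from. Assumed: 20 v 20 patients, all completing; two-sided alpha 0.05; within-group baseline to follow-up correlation r of 0.3, 0.5 or 0.7; for power only, a true effect of 0.9 SD. Results are in SDs of the outcome.

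**Variance.** In large samples ANCOVA multiplies the unadjusted variance by 1 − r². Estimating the slope costs a further factor 1 + 1/(N − 4) = 1 + 1/36 = 1.028.

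| r | 1 − r² | × 1.028 | Equivalent unadjusted N = 40/factor |
|---|---|---|---|
| 0.3 | 0.91 | 0.935 | 42.8 |
| 0.5 | 0.75 | 0.771 | 51.9 |
| 0.7 | 0.51 | 0.524 | 76.3 |

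The net cuts are 6%, 23% and 48%. Variance breaks even at r = √(1 − 1/1.028) = 0.164.

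**Expected 95% interval half-width, 20 per arm.**

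- ANOVA of follow-up values: t(38) × √(2/20) = 0.640.
- ANCOVA: t(37) × √[(1 − r²)(2/20)(1 + 1/36)].
- ANOVA of change scores: 0.640 × √[2(1 − r)].

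| r | ANCOVA | Ratio to ANOVA | Change score: ratio to ANOVA |
|---|---|---|---|
| 0 | 0.650 | 1.015 | 1.414 |
| 0.1 | 0.646 | 1.010 | 1.342 |
| 0.3 | 0.620 | 0.968 | 1.183 |
| 0.5 | 0.563 | 0.879 | 1.000 |
| 0.7 | 0.464 | 0.725 | 0.775 |

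Interval width breaks even at r = 0.17 (0.18 with 18 per arm, 0.19 with 16).

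**Simulation** (bivariate normal, 100,000 runs per cell). Mean half-widths were 0.636 for ANOVA, 0.615/0.559/0.460 for ANCOVA and 0.752/0.636/0.492 for change scores at r = 0.3/0.5/0.7. Power at 0.9 SD:

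| r | ANOVA | ANCOVA | Change score |
|---|---|---|---|
| 0.3 | 79.2% | 81.7% | 64.8% |
| 0.5 | 79.2% | 88.3% | 79.1% |
| 0.7 | 79.2% | 96.8% | 94.8% |

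At r = 0.1 ANOVA had 79.5% and ANCOVA 78.7%. With a real coin flip (exactly 20/20 occurs with probability 12.5%), ANOVA had about 78% and ANCOVA 80.7%/87.7%/96.5%. With no effect, every method rejected in 4.9% to 5.2% of runs.

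**Chance imbalance.** The difference in baseline means has SD √(2/20) = 0.316. A difference of that size shifts the estimate from follow-up values by 0.316 × r = 0.09, 0.16 or 0.22 SD at r = 0.3, 0.5, 0.7.

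**Fellow-eye reading (40 pairs).** Let r be the correlation between the between-eye difference at screening and at follow-up. The half-width ratio is then [t(38)/t(39)] × √[(1 − r²)(1 + 1/37)] = 0.968, 0.878 and 0.724 at r = 0.3, 0.5, 0.7, with break-even at 0.167. These cuts need between-eye differences that persist over time. If only patient-level differences persist, pairing has already removed them and the baseline term adds nothing.

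**The case against.** The strongest objection is that section 7.2 is underspecified rather than wrong. Section 3.1 describes the testing as a series that starts before surgery: "Patients undergoing cataract surgery will have dry eye testing prior to surgery, 1 week after surgery, and 3 weeks after surgery". The ANOVA could therefore be a repeated-measures model with screening as one time point, or an analysis of change. This stands as a point about reading, and it affects the size. Against change scores at r = 0.7, ANCOVA's interval is only about 6% narrower (0.460 v 0.492), and the 0.09/0.16/0.22 SD shifts no longer apply. It does not remove the point. The group-by-visit contrast between screening and a follow-up visit is in essence the change-score comparison, which ANCOVA matches or beats in large samples. At r = 0.3 the gap is larger (0.615 v 0.752).

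Second, the size rests on assumptions. The correlation and the 0.9 SD effect are not in the documents. The simulations are normal, while staining is a bounded grade. Section 4.2 excludes central staining and osmolarity above 340, which narrows the baseline range and can lower the correlation. Section 7.3 analyses completers only. All this stands. In a separate 10,000-run check the ANCOVA interval was the narrower one in 47% of trials at r = 0.2, 69% at 0.3 and 96% at 0.5. The gain is probable, not assured.

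Third, the patient-or-eye ambiguity comes first. Section 5.3 puts DEXYCU in one eye of patients having bilateral surgery. If fellow eyes are compared, pairing must be modelled and a single added covariate is not enough. This also stands, so the fix has to cover both designs.

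Finally, this is a single-centre pilot with no power target to miss. That limits the priority but does not justify leaving collected information unused.

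**Conclusion.** The point holds. The plan specifies no adjustment for a valid pre-randomisation covariate that it already collects for both primary endpoints. The consequence is lost precision, not bias or an inflated error rate.

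For parallel groups of 20 v 20 completers, and if follow-up values are compared, ANCOVA narrows the expected interval by about 3%, 12% and 28% at assumed correlations of 0.3, 0.5 and 0.7. It gains nothing below about 0.17, and the worst case is about 1.5% in width (under 3% in variance). That asymmetry is why the change is worth making even though the correlation is unknown.

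The omission and the direction of the effect are well supported; the size is not fixed by the documents. It is smaller against change scores at high correlation, and could be nil in a fellow-eye design. This is a recommended improvement, not a condition for a valid analysis.

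**What to change.** First state whether the unit of comparison is the patient or the eye. Then, in section 7.2, specify for each primary endpoint an ANCOVA at one named post-operative visit, with treatment as factor and the same eye's screening value of that measure as covariate. Report the adjusted mean difference with its 95% confidence interval. If both eyes of a patient contribute, use a mixed model with the same covariate and a patient effect.

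Because staining is a bounded 0-15 grade, a rank-based or ordinal sensitivity analysis is a sensible addition, though the baseline adjustment does not depend on it.

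The cost is a sentence or two in 7.2 and one extra model term, slightly more if the two-eye model is needed. No visits, measurements or patients are added. The statistical price is under 3% in efficiency if the baseline correlation turns out close to zero. The model should be fixed before outcome data are seen, so that the choice between follow-up values, change scores and adjustment is not made afterwards.

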7.3 Subject Population(s) for Analysis

All patient who met inclusion criteria and complete the study will be included in the selection of subjects to be included in the analyses.

8 Safety and Adverse Events

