4.4 Early Withdrawal of Subjects

Subjects will be carefully monitored after surgery, including visual acuity measurements, intraocular pressure measurements, anterior and posterior segment evaluation, as well as dry eye testing. If patients have an intraocular pressure elevation over 35mm that requires additional medication, they will be withdrawn from the study. Also, if patients require a deviation from the standard cataract postoperative regimen, they will be withdrawn from the study.

5 Investigational Product

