5.4 Subject Compliance Monitoring

The study team will assess and track compliance on each study visit (1 day, 1 week, 3 weeks). At all postoperative visits, the study team will monitor adherence to the eyedrop regimen. If there is a significant deviation from the eyedrop regimen, the principal investigator will determine continuation in the study.

A case report binder will be created for each subject in the study. Binder tabs will include:

- Screening Visit
- Day 1 Visit
- Day 7 Visit
- Day 21 Visit
- Exit Form
- Early Exit Visit
- Nonserious Adverse Event Forms
- Serious Adverse Event Forms

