8.5 Stopping Rules

Upon completion of the study, an "Exit Form" will be completed and signed by the Principal Investigator. Patients who withdraw early from the study will complete an "Early Exit Visit" form detailing the last visit and reasons for early withdrawal.

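### The only analysis set is completers, while patients are withdrawn for post-treatment events that may differ by group, so randomisation does not protect the comparison

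*Combined protocol and SAP*

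**What the plan says.** Section 7.3 gives the whole definition of the analysis population: "All patient who met inclusion criteria and complete the study will be included in the selection of subjects to be included in the analyses". No all-randomised set, missing-data method or sensitivity analysis appears. Section 7.2 names only an ANOVA between the groups.

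Four other parts of the document decide who completes:

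- **Section 4.4, pressure:** "If patients have an intraocular pressure elevation over 35mm that requires additional medication, they will be withdrawn from the study".
- **Section 4.4, regimen:** "if patients require a deviation from the standard cataract postoperative regimen, they will be withdrawn from the study".
- **Section 5.4:** "If there is a significant deviation from the eyedrop regimen, the principal investigator will determine continuation in the study". No masking of the investigator is described.
- **Section 8.5:** withdrawn patients complete a "form detailing the last visit and reasons for early withdrawal". Nothing is said about later visits or about using values already recorded.

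Section 5.3 places randomisation after screening and before first-eye surgery, so every one of these events follows randomisation. On measurement, section 6 says: "At all visits, visual acuity, eye pressure measurements, tear film osmolarity, and corneal staining will be measured and recorded".

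**The concern.** Randomisation makes the two groups comparable as assigned. It does not make the survivors of a post-treatment filter comparable. The filter distorts the comparison if withdrawal is related to the outcome and works differently in the two groups, either in how often it happens or in why.

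The protocol gives grounds for thinking the groups could differ. Section 1.6 lists pressure increases and iritis among the most common DEXYCU reactions, at 5-15%. In the other direction, an intraocular steroid could reduce inflammation-driven regimen changes. Section 2 describes dry eye as inflammatory, so those changes may be related to osmolarity and staining. The net sign is therefore unknown.

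Investigator discretion over continuation, with no masking described, is a second route to selection. The design wording, "in one eye or the STANDARD group (standard postoperative cataract regimen", leaves open whether fellow eyes are compared. If they are, withdrawing a patient removes both eyes.

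At stake is whether an observed difference, or the lack of one, on the two primary endpoints can be attributed to DEXYCU. Under the present text a reader could not separate treatment from selection.

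**Working it through.** **Inputs from the documents.** 40 patients (7.1), completers only (7.3), and a reaction rate of 5-15% on DEXYCU (1.6), which is 1 to 3 of 20 patients. That rate is an upper guide for the pressure trigger, because it covers any pressure increase and not only those over 35mm. The documents give no control rate, no rate of required regimen changes, no correlation between these events and the endpoints, no alpha and no allocation ratio. The plan states no figure for bias, so there is none to reproduce.

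**Assumptions.** Two-sided 5% test, 20 per group, outcome SD = 1, higher = worse, no true effect. A patient is lost when a latent variable, correlated r with the outcome, falls in its upper tail of probability p.

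**Formula.** The completer mean in a group shifts by

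m(p, r) = −r × φ(z) / (1 − p), where z is the (1 − p) normal quantile.

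Bias = m for DEXYCU minus m for STANDARD. A positive value means DEXYCU looks worse.

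| p | φ(z)/(1 − p) | m at r = 0.5 |
|---|---|---|
| 5% | 0.1031/0.95 = 0.109 | −0.054 |
| 10% | 0.1755/0.90 = 0.195 | −0.097 |
| 15% | 0.2332/0.85 = 0.274 | −0.137 |
| 20% | 0.2800/0.80 = 0.350 | −0.175 |

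For the stress case, p = 30% and r = 0.7 give −0.7 × 0.3477/0.70 = −0.348.

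**Parallel groups.** Type I error comes from 20,000 simulated null trials per setting, with a pooled t-test on completers.

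| Loss, DEXYCU v STANDARD | Bias (SD) | Type I error |
|---|---|---|
| 10% v 10%, both r 0.5 | 0.00 | 5.1% |
| 10% v 20%, both r 0.5 | −0.097 + 0.175 = +0.08 | 5.5% |
| 10% random v 20% at r 0.5 | 0 + 0.175 = about +0.17 | 7.8% |
| 5% at r 0.5 v none | −0.05 | 5.4% |
| 10% at r 0.5 v none | −0.10 | 6.1% |
| 15% at r 0.5 v none | −0.14 | 6.9% |
| Stress: 10% random v 30% at r 0.7 | +0.35 | about 16% |

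Swapping the groups reverses the sign. Equal loss rates do not guarantee safety: 15% in each group, random in one and r = 0.5 in the other, still gives 0.137 SD. Balanced withdrawal counts alone would therefore not settle the matter.

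**Fellow eyes.** Take 40 pairs, with a pair lost if either eye is lost. Removing the pair also shifts the other eye, by the inter-eye correlation k, so the bias is multiplied by about (1 − k).

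- 10% random v 20% at r 0.5: 0.175 × 0.5 = 0.09 SD at k = 0.5 and 0.175 × 0.3 = 0.05 SD at k = 0.7. Simulated type I error is 7.5% and 6.3%. Pairs left: 40 × 0.9 × 0.8 = 28.8.
- Stress case: 0.17 SD at k = 0.5 and 0.10 to 0.11 SD at k = 0.7. Simulated type I error is about 14% and 10%.

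**The case against.** The strongest reply is that the effect is probably small. The pressure trigger needs two things together, a reading over 35mm and a need for additional medication. The 5-15% is for any increase, comes from other trials and has no control rate beside it. Nothing in the documents links pressure to osmolarity or staining. Losing 2% of one group at r = 0.5 gives about 0.02 SD and 5.1% type I error. Both groups also receive a topical steroid, "topical prednisolone acetate 1% qid and topical gatifloxacin qid for 1 week", which may narrow any difference in inflammation-driven changes, and iritis matters here only if it forces a regimen change. This is a 40-patient pilot. With 20 per group, 80% power needs √(2/20) × (1.96 + 0.84) = 0.89 SD, well above the biases shown. All of this stands. It limits the severity and is why the stress case should not be read as a forecast. It does not make the completer set sound: regimen changes have no stated rate, and the plan would not show which case had occurred.

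A second reply is that an Early Exit Visit form has its own binder tab, so an exit measurement may be intended. That is possible. But section 6 lists only four visits, and an exit value would not replace Day 7 or Day 21.

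A third is that osmolarity is read on an instrument, and that 4.4 may concern clinical need while 5.4 concerns adherence. Investigator discretion affects who stays, not the reading itself. The split between the two sections is a reasonable guess, but the text does not state it.

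**Conclusion.** The concern holds and should be fixed. That the plan analyses completers only, after withdrawals triggered by post-randomisation events, is certain from the text. That the resulting bias is material is not established: every loss rate and correlation above is an assumption, as are the 5% level and 20 per group. Under moderate assumptions the null error rate is about 5% to 8% and the spurious difference at most about 0.17 SD, in either direction. The roughly 16% figure needs 30% selective loss in one group, r = 0.7 and purely random loss in the other. If the comparison is between fellow eyes, the bias is smaller.

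**What to change.** - **Section 7.3:** define the primary analysis as every randomised patient or eye that had surgery, in the assigned group, using all available Day 7 and Day 21 values whether or not additional medication was used. Those never operated on have no postoperative values, but they should still be counted. Make completers a secondary, descriptive analysis.
- **Reporting:** by group, give the numbers randomised, operated, withdrawn (with reason) and missing at each visit.
- **Missing values:** add one sensitivity analysis, with its imputation method named. An example is a tipping-point analysis that shifts the imputed values separately by group.
- **Sections 4.4 and 5.4:** state that the triggers are recorded but do not end Day 7 and Day 21 dry eye data collection. This leaves clinical care as it is. Reconcile the two sections so that it is clear which rule covers which kind of deviation.

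The cost is wording, plus keeping two visits that section 6 already schedules for the few patients concerned. One drawback is that some values will be measured under additional medication, which can blur a group difference. Dropping those patients does not solve that problem. Values not collected at the time cannot be recovered later.

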8.1 Definitions

An adverse event is any untoward medical occurrence in a patient who is administered a test article (DEXYCU). The adverse event does not necessarily have a causal relationship with the treatment. An adverse event can therefore be any unfavorable and unintended sign, symptom, or disease temporally associated with the use of the test article, whether or not related to the test article.

A nonserious adverse event is defined as a change in a patient's ophthalmic and or medical health that is not life-threatening, does not require hospitalization, does not prolong a current hospitalization and is not disabling. Nonserious adverse events must be reported by use of a Nonserious Adverse Event Form and may also be reported by a telephone call. All nonserious adverse events must be reported on a Nonserious Adverse Event Form whether they are considered related or unrelated to the test article.

A serious adverse event is defined as any adverse experience occurring at any dose that results in any of the following outcomes: death; a life threatening adverse event, inpatient hospitalization, prolongation of existing hospitalization, or a persistent or significant disability/incapacity.

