1.6 Risk/Benefits

The following adverse events rates are derived from three clinical trials in which 339 patients received the 517 microgram dose of DEXYCU. The most commonly reported adverse reactions occurred in 5-15% of subjects and included increases in intraocular pressure, corneal edema, and iritis. Other ocular adverse reactions occurring in 1-5% of subjects included, corneal endothelial cell loss, blepharitis, eye pain, cystoid macular edema, dry eye, ocular inflammation, posterior capsular opacification, blurred vision, reduced visual acuity, vitreous floaters, foreign body sensation, photophobia, and vitreous detachment.

2 Study Objectives

The objective of this clinical research is to evaluate whether the signs and symptoms of dry eye after cataract surgery improve with the addition of a DEXYCU intraocular injection. Multiple studies have established that dry eye worsens after cataract surgery. There is also

a strong body of evidence that shows that dry eye is inflammatory. The objective of this study is to evaluate whether the intraocular use of steroid impacts dry eye.

3 Study Design

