8.2 Recording and Reporting of Adverse Events

An Adverse Event Form must be completed for all serious adverse events within 24 hours of the investigator's knowledge of the event and to the Institutional Review Board according to their requirements.

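### Section 8.1 has no sight-threatening or important-medical-event criterion, so an ocular complication that threatens sight but is not yet significantly disabling falls outside the 24-hour report

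*Combined protocol and SAP*

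**What the plan says.** Section 8.1 defines a serious event by its outcome. It must be "any adverse experience occurring at any dose that results in any of the following outcomes", and the list is: "death; a life threatening adverse event, inpatient hospitalization, prolongation of existing hospitalization, or a persistent or significant disability/incapacity". That makes five outcomes, and none is specific to the eye.

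The same section defines a nonserious event as a change in ophthalmic or general health that "is not life-threatening, does not require hospitalization, does not prolong a current hospitalization and is not disabling". Ophthalmic changes are therefore expressly within the nonserious class.

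The reporting rules differ by class. Section 8.2 states: "An Adverse Event Form must be completed for all serious adverse events within 24 hours of the investigator's knowledge of the event", and adds reporting to the Institutional Review Board according to the board's requirements. For the other class, Section 8.1 states: "Nonserious adverse events must be reported by use of a Nonserious Adverse Event Form and may also be reported by a telephone call". It gives no time limit.

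Section 1.6 describes the product's known risks: "The most commonly reported adverse reactions occurred in 5-15% of subjects and included increases in intraocular pressure, corneal edema, and iritis". Further ocular reactions, among them cystoid macular edema, endothelial cell loss and reduced visual acuity, are put at 1-5%.

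**The concern.** The product is placed inside the eye at the end of eye surgery, so the foreseeable harms are ocular. The seriousness test is a general-medicine one. Apart from the disability outcome, it depends on death, danger to life or hospital admission. A complication that endangers sight need involve none of these if it is treated as an outpatient.

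What is at stake is how quickly such an event is reported and whether the serious-event report to the Institutional Review Board is made. Prompt reporting is most useful while the threat to sight has not yet become a loss of sight. On the text, that is the period in which neither is required.

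**Working it through.** No arithmetic applies, since the point concerns a definition and the reporting rule tied to it. The check applies the stated criteria to one type of event: an ocular complication that threatens sight, is treated without admission, and is not, or not yet, significantly disabling.

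**Step 1: serious outcomes (Section 8.1)**

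| Outcome | Met? |
|---|---|
| Death | No |
| Life-threatening | No: sight is at risk, not life |
| Inpatient hospitalization | No: treated without admission |
| Prolonged hospitalization | No |
| Persistent or significant disability/incapacity | No, by the terms of the case |

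The wording requires the event to result in a listed outcome. A threat to sight is not listed, and neither is treatment given to prevent lasting harm.

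**Step 2: nonserious limbs (Section 8.1)**

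| Limb | Met? |
|---|---|
| Not life-threatening | Yes |
| No hospitalization required | Yes |
| No hospitalization prolonged | Yes |
| Not disabling | Yes, reading this as the mirror of the serious criterion |

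The last row depends on that reading. Taken literally, an event that is mildly and briefly disabling would fit neither definition. It would still miss the 24-hour rule, because that rule requires a serious event.

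**Step 3: reporting.** The 24-hour form and the board report in Section 8.2 apply to serious events. This event goes on the nonserious form, with an optional telephone call and no stated deadline.

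**Step 4: does anything else close the gap?**

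- Section 4.4 withdraws a patient whose pressure rises above 35mm and needs additional medication. This is the plan's only event-specific ocular threshold, and it is not linked to seriousness or to the 24-hour rule.
- Section 6 has visual acuity and eye pressure recorded at every visit, but attaches no reporting category to them.
- Section 8.5 is headed as stopping rules but deals only with exit forms.
- Section 8.6 refers monitoring back to the protocol and the case report binder.
- Sections 5.4 and 9.2 list the two kinds of adverse event form without adding a criterion for choosing between them.

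No other section adds a seriousness criterion.

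**The case against.** The strongest objection concerns the disability outcome. A reader might infer that any sight-threatening complication treated as an outpatient is nonserious unless vision is permanently lost. The text does not support that. It says persistent *or* significant, so a significant incapacity need not be lasting. An infection or corneal decompensation that already markedly reduces vision can qualify as serious at once, and it can also fail the requirement that a nonserious event not be disabling. This part of the objection stands and limits the point to events short of significant disability.

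A second tempting step is to put a number on the problem from Section 1.6. Assume that 5-15% applies to each common reaction and that 20 to 40 eyes are injected, since the randomization wording allows either a between-patient or a within-patient reading of 40 patients. That gives 0.05 × 20 = 1 to 0.15 × 40 = 6 expected events per reaction. But those rates come with no severity, and Section 1.6 names neither intraocular infection nor corneal decompensation. The product counts reactions of any severity. It does not measure misclassified events and should not be used as their number.

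Third, a reader might infer that the trial would reach a wrong safety conclusion. Section 3.2 lists no safety endpoint and Section 7.2 plans no safety analysis, so no planned conclusion rests on the serious-event count. The events are not lost either. Every nonserious event needs a form whether or not it is thought related, and a withdrawal leaves an early-exit form with reasons. In a single-center study that the principal investigator monitors weekly, that investigator is likely to know of the event anyway. These routes narrow the gap, but none of them carries the 24-hour deadline.

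Finally, some of the record cannot be seen. Section 9.2 says copies of the source documents are included, but they are not in the text supplied, and the Institutional Review Board's own requirements are not given. Either might contain a deadline or a broader trigger. The statement that there is no deadline is therefore confined to the protocol text.

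**Conclusion.** The point holds in a limited form. Under the stated rules, an ocular complication that threatens sight, is managed without admission, and is not or not yet significantly disabling is recorded as nonserious and does not trigger the 24-hour form or the serious-event report to the Institutional Review Board. If the event later becomes significantly disabling, the 24-hour period may start only when that is recognised.

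The number of events affected is unknown, because the documents give no rate for sight-threatening complications. The effect is on classification and speed of reporting. Sample size and the efficacy analysis are not affected. If a count of serious events is reported, a zero would be compatible with sight-threatening complications having occurred, so the count should be read together with the definition behind it.

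The conclusion rests on two assumptions: that staff choose between the two forms by the definitions in Section 8.1, and that the unseen forms and board requirements do not supply the missing criterion. It is worth correcting because the gap lies in the organ being treated and the remedy is short.

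**What to change.** Make two wording changes in Section 8.1:

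- Add to the serious outcomes: 'or an important medical event that, in the investigator's judgment, is sight-threatening or requires intervention to prevent permanent impairment of vision'.
- Add to the nonserious definition: 'is not sight-threatening'.

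Leave the 24-hour rule in Section 8.2 unchanged; it then applies to these events automatically.

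The cost is some additional expedited forms. How many cannot be stated from the documents, and a loose reading of the intervention clause could bring in routine, medically treated events. Framing the criterion as an important medical event judged by the investigator is meant to limit that. The change affects classification and reporting only, and patient treatment stays the same.
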